### Potential benefits

Contingency management has been shown to effectively reduce relapse rates in those with substance abuse disorder, yet the specific underlying neurobiological mechanism of action for abstinence using this procedure is currently unknown. While other researchers have examined the effect of strengthening cognitive control of impulses in the executive function system of the prefrontal cortex, contingency management conversely aims to introduce new conditioned schedules within the mesolimbic reward system. Thus, we aim to see whether the receipt of money, as opposed to drugs can become more salient, and thus be linked to function of the reward system in those who have been dependent on MA.

We do not anticipate any benefits to participants in the non-substance-using control condition.

### Importance of the knowledge to be gained

Information gathered from this study will help to determine whether socially regulated gene expression can serve as a clinically meaningful, non-abstinence-based endpoint for contingency management (CM) for MUD in MSM living with HIV. The potential benefit of this measure as a non-abstinence endpoint to CM for MUD is that it provides information about both psychosocial health and the underlying stress-biology that exacerbates risk of chronic disease. Both of these aspects of health are important to understanding substance use treatment efficacy on a holistic level. Promoting psychosocial health and reducing distress may be important to long-term recovery from MUD, especially for PLWH with MUD. Assessing molecular patterns

linked to MA use and pathogenesis may help in identifying risk and preventing development of MA-related chronic disease. Moreover, identification of a clinical endpoint beyond abstinence may facilitate future approval of therapies for MUD.

### 3 STUDY OBJECTIVES

#### 3.1 Primary Objective

To investigate whether changes in CTRA gene expression coincide with changes in MA use and viral load over the course of 12 weeks in HIV-positive MSM with and without MUD.

#### 3.2 Secondary Objectives

- To investigate whether differences in seven psychosocial dimensions of drug addiction (Short Inventory of Problems Revised (SIP-R))—physical, social, intrapersonal, interpersonal, impulse control—are associated with differences in CTRA gene expression.
- To conduct an exploratory pilot investigation to determine the degree to which CTRA mediates the association between MA use and viral suppression.

### 4 STUDY DESIGN

#### 4.1 Study Overview

The proposed study will be a two-arm clinical trial design of 55 MSM living with HIV, of whom 35 HIV-positive MSM with MUD (MA+/HIV+) will receive contingency management for MA reduction, and 20 HIV-positive, non-substance-using MSM (MA-/HIV+) will participate as a control. There is extensive evidence that CM has greater efficacy than a non-contingent condition in the treatment of MUD (41-44, 46-49, 88), so it may raise ethical concerns to withhold CM from people with MUD who are willing to receive treatment. For this reason, this study uses a control of non-substance using HIV-positive (MA-/HIV+) MSM rather than a non-contingent yoked control of HIV-positive MSM with MUD (89). The use of a non-substance-using HIV-positive control will provide a baseline level of CTRA among HIV-positive MSM who do not have MUD or use other substances, which can be compared against CTRA levels in those with MUD. Screening data will be reviewed to determine subject eligibility. Subjects who meet all inclusion criteria and none of the exclusion criteria will be entered into the study. The following treatment regimens will be used:

- Contingency management twice weekly for 8 weeks, with post-treatment follow-up at Week 12.

- Non-substance-using control will not receive a treatment, but will be evaluated at Baseline, Weeks 4, 8, and 12.

The total duration of subject participation will be 14 weeks. The total duration of the study is expected to be 4 years: 1 year of rolling subject recruitment, 1 year for final subject follow-up, 1 year of biospecimen processing, and 1 year of analysis.

## **5 CRITERIA FOR EVALUATION**

### **5.1 Primary Efficacy Endpoint**

The primary efficacy endpoint is a gene expression pattern called the conserved transcriptional response to adversity (CTRA), measured using transcriptome profiling of leukocytes. We will test whether this gene expression pattern coincides with changes in MA use and psychosocial domains of addiction severity.

### **5.2 Secondary Efficacy Endpoints**

We will conduct negative urine tests for MA as a measure of abstinence. HIV viral load from will be quantified from plasma.

### **5.3 Safety Evaluations**

We will evaluate patients on MA use patterns using thrice weekly urine tests. Viral load will be taken at baseline, Week 4, Week 8, and Week 12 to determine HIV disease progression. We will report on incidence of adverse events

### **5.4 Other Evaluations**

We will assess psychosocial problems with substance use using the Short Inventory of Problems-Revised (SIP-R). Sociodemographics – age, race, education level, sexual orientation, housing status, body mass index (BMI), smoking history, and heavy alcohol use history.

## **6 SUBJECT SELECTION**

### **6.1 Study Population**

We plan to recruit 55 cisgender men who have sex with men (MSM) aged 18-45 living with HIV (confirmed by certification or by a 5th generation HIV screening assay) who reside in Los Angeles County who enroll into this study. Of these participants, 35 must meet the DSM-5 criteria for methamphetamine (MA) use disorder (MUD) (via Structured Clinical

Interview for DSM-5 (SCID-5)) and have a positive urine test for METH during screening (MA+/HIV+), and 20 participants must qualify as a non-substance-using control (MA-/HIV+).

## 6.2 Inclusion Criteria

### HIV-positive MSM with MUD in the contingency management condition (N = 35)

1. Assigned male sex at birth
2. 18 to 45 years of age
3. Reports having sex with men in the past 12 months.
4. HIV-positive (confirmed by certification or by HIV rapid test)
5. Has an HIV care provider (last seen in the past 12 months)
6. Has a current antiretroviral prescription
7. Meets the DSM-5 criteria for MUD using SCID-5
8. Urine test is positive for MA within 30 days of their screening visit
9. Seeking treatment for MUD.
10. Ability to attend twice weekly appointments for drug testing and treatment

### HIV-positive MSM non-substance-using control (N = 20)

1. Assigned male sex at birth
2. 18 to 45 years of age
3. Reports having sex with men in the past 12 months.
4. HIV-positive (confirmed by certification or by HIV rapid test)
5. Has an HIV care provider (last seen in the past 12 months)
6. Has a current antiretroviral prescription

### **6.3 Exclusion Criteria**

#### HIV-positive MSM with MUD in the contingency management condition (N = 35)

1. Identifies as (cis- or transgender) female
2. Reports another current or past substance use disorder
3. Reports being in another intervention or clinical trial for substance use
4. Positive test for opioids and/or cocaine

#### HIV-positive MSM non-substance-using control (N = 20)

1. Identifies as (cis- or transgender) female
2. Positive test for MA, opioids, cocaine, and/or MDMA.
3. Reports substance use (MA, opioids, cocaine, MDMA, hallucinogens, heavy alcohol use, and/or tobacco) in the past 6 months
4. Reports past or current substance use disorder

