## 8 STUDY TREATMENTS

### 8.1 Method of Assigning Subjects to Treatment Groups

This is a non-randomized behavioral trial with a non-substance-using control group. HIV-positive MSM with methamphetamine use disorder who meet the criteria described above will be assigned to the contingency management treatment group. HIV-positive MSM who do not use substances and meet the criteria described above will be assigned to the non-substance-using control group.

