### 15.2 Demographic and Baseline Characteristics

Sociodemographic and behavioral covariates will include age, race, education level, sexual orientation, employment, income, body mass index (BMI) which is a known risk factor for inflammatory gene expression and a standard biological covariate in social genomics analysis (11, 98-100), smoking history, heavy alcohol use history.

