### 15.3 Analysis of Primary Endpoint

Using mixed effects linear regression and marginal plots, we will estimate, graph, and compare trajectories of CTRA gene expression between those with methamphetamine use disorder in the contingency management (MA+/HIV+) and non-substance-using control (MA-/HIV+) conditions.

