### 15.6 Multivariate Analysis for Associations Between Endpoints

Associations between MA use, CTRA gene expression, and viral suppression. All models in Aim 1 will adjust for age, race, education, employment, housing, and mRNA encoding markers of major leukocyte subsets (e.g., CD4). We will also assess for confounding by COVID-19 infection detected by immunoassay, liver function, and type of ART prescription. MA use and CTRA. Using a linear mixed effects regression, we will test whether a negative MA urine test is associated with reductions in CTRA contrast scores across four time points—Visits B, 4.2, 8.2, and 12.0. We will use a time (days) by MA urine result interaction term to estimate difference in change in CTRA as

a function of MA test result. CTRA and viral load. Using a mixed effects logistic regression, we will test whether CTRA gene expression is associated with viral suppression (<200c/mL) across three time points—Visits B, 4.2, 8.2, and 12.0. We will include a time (days) by CTRA gene expression interaction term to test this association longitudinally. We will also test whether CTRA and viral load are reciprocally associated using dynamic panel data modeling with maximum likelihood (102-104). This approach will allow us to simultaneously test whether CTRA is associated with viral load at subsequent observations, and account for whether CTRA is affected by prior values of viral load (102-104).

**Associations between psychosocial indicators of substance use severity and CTRA.** Using a linear mixed effects regression, I will test whether the seven domains of the Addiction Severity Index (ASI) is associated with reductions in CTRA contrast scores across four time points—Visits B, 4.2, 8.2, and 12.0. I will use a time (days) by ASI domain score interaction term to estimate change in CTRA as a function of changes in ASI scoring. We will control for age, race, education, and mRNA markers of major leukocyte subsets.

**Indirect associations between MA use, CTRA, and viral suppression.** I will use propensity scores to test the degree to which CTRA mediates the association between MA use and viral suppression (105, 106). The general theory is that we would compute propensity score for CTRA—the probability of having a particular CTRA level—to compare participants who used MA with those who would have had the same value of the CTRA had they used MA.

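### Recent tobacco and heavy alcohol use is barred in controls but not in the CM arm, and 15.2, 15.3 and 15.6 do not agree on adjusting the CTRA analyses for it

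*Combined protocol and SAP*

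**What the plan says.** Arm is set by substance-use status. Section 8.1 states: "This is a non-randomized behavioral trial with a non-substance-using control group".

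In section 6.3, control exclusion 3 removes anyone who "Reports substance use (MA, opioids, cocaine, MDMA, hallucinogens, heavy alcohol use, and/or tobacco) in the past 6 months". The CM list in the same section bars a man who "Reports another current or past substance use disorder", a man in another substance-use intervention or trial, and a "Positive test for opioids and/or cocaine". The synopsis adds MDMA to that last item. Neither version of the CM list mentions tobacco or heavy alcohol use.

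Section 4.1 gives the purpose of the control: a baseline CTRA level among HIV-positive MSM "who do not have MUD or use other substances, which can be compared against CTRA levels in those with MUD". Section 15.3 then plans to "compare trajectories of CTRA gene expression between those with methamphetamine use disorder in the contingency management (MA+/HIV+) and non-substance-using control (MA-/HIV+) conditions" by mixed effects linear regression, with no covariates named.

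On adjustment, section 15.2 ends its covariate list with "smoking history, heavy alcohol use history" but ties the list to no model. Section 15.6 says: "All models in Aim 1 will adjust for age, race, education, employment, housing, and mRNA encoding markers of major leukocyte subsets". It adds a check for confounding by COVID-19 infection, liver function and ART type. Tobacco and alcohol are in neither part.

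**The concern.** Two men with the same tobacco or alcohol use are treated differently at entry. One with MUD and no other reported use disorder is admitted; one without MUD is turned away. Nothing else in the design balances this, because assignment is not random.

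If tobacco or heavy drinking shifts CTRA in either direction, the shift falls wholly on the CM side of the comparison. Sections 15.3 and 15.6, followed as written, would leave it there. An arm difference could then be credited to MUD when part of it belongs to tobacco or alcohol; a shift in the opposite direction could hide a real MUD difference.

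The same exposure can enter the urine-result models of the synopsis and section 15.6 if controls are pooled into them. Controls would contribute mainly MA-negative observations from men without recent tobacco or heavy alcohol use, so the between-person part of the urine-result coefficient would carry it. Section 15.7 counts all 55 participants in its person-observations, which points towards pooling.

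**Working it through.** **Plan's own figure.** There is none for this contrast. Section 15.7 sizes the association models in person-observations and gives no power or detectable difference for CM against control.

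**Inputs from the documents.** 35 CM participants and 20 controls (section 4.1). Reported past-6-month tobacco or heavy alcohol use is 0% among controls (control exclusion 3).

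**Assumptions, not in the documents.** Share of the CM arm exposed, s = 40%, 60% or 80%. Effect of exposure on CTRA, d = 0.2, 0.3 or 0.5 SD. Two-sided 5% test, no true MUD effect, no adjustment, full retention, a single-visit comparison of means in SD units.

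**Bias.** The gap created by exposure alone is (s − 0) × d.

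**Standard error.** √(1/35 + 1/20) = √0.0786 = 0.280 SD.

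**Rejection rate.** Φ(bias/0.280 − 1.96) + Φ(−bias/0.280 − 1.96).

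| CM exposed | Effect (SD) | Bias (SD) | Rejection rate |
|---|---|---|---|
| 40% | 0.2 | 0.08 | 5.9% |
| 40% | 0.3 | 0.12 | 7.1% |
| 40% | 0.5 | 0.20 | 11.0% |
| 60% | 0.2 | 0.12 | 7.1% |
| 60% | 0.3 | 0.18 | 9.8% |
| 60% | 0.5 | 0.30 | 18.8% |
| 80% | 0.2 | 0.16 | 8.8% |
| 80% | 0.3 | 0.24 | 13.7% |
| 80% | 0.5 | 0.40 | 29.7% |

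For the mean of four visits with an assumed within-person correlation of 0.5, the standard error is multiplied by √((1 + 3 × 0.5)/4) = 0.79, and the two ends of the range become 6.5% and 43.9%.

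For scale, the single-visit difference detectable with 80% power is (1.96 + 0.84) × 0.280 = 0.79 SD.

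**Precision when CM non-users are compared with the 20 controls.**

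- 40% exposed, 21 non-users: √(1/21 + 1/20) = 0.31 SD
- 60% exposed, 14 non-users: √(1/14 + 1/20) = 0.35 SD
- 80% exposed, 7 non-users: √(1/7 + 1/20) = 0.44 SD

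**What adjustment can do.** Among controls the exposure covariate is always zero, so its coefficient is estimated from the CM arm alone. With one combined yes/no exposure and no other covariates, there are three filled cells (control, CM unexposed, CM exposed) and three parameters. The adjusted arm difference at one visit is then the difference between CM non-users and controls, at the standard errors just given. Adjustment is possible, but it is not free.

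**The case against.** The best case for the plan has six parts.

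- **A non-using control is intended.** Section 4.1 says so and the arm is named accordingly. This stands. A reader might infer that the control entry rule is itself a mistake and should be relaxed. The documents do not support that: overlap in smoking would be gained at the expense of the control's stated purpose. What remains is how the contrast is adjusted and described.
- **Section 15.2 signals an intent to adjust.** This stands in part, so it would be wrong to say that the plan ignores tobacco and alcohol. But 15.3 does not take up the list, and the explicit list in 15.6 leaves both out. The coding of the history items is not given, so whether they capture use in the past 6 months cannot be told. Section 15 promises a detailed SAP, where this can be settled.
- **The arm comparison is not clearly the main analysis.** The synopsis calls the study within-subjects, and its primary analysis plan is a urine-result-by-time model. Section 15.3 compares trajectories, and stable smoking or drinking shifts level more than slope. This stands and limits the reach of the point. However, 15.3 is headed as the analysis of the primary endpoint, does not say whether level or slope is the target, and 4.1 describes a comparison of levels.
- **The CM exclusion for another use disorder removes some exposed men.** True, by an unknown amount. It relies on report, and use without a reported disorder passes.
- **The size is assumed.** True. At the mild end the false-positive rate is about 6%, barely above nominal.
- **The mechanism is not established in the documents.** A reader might infer a strong effect because CTRA is mostly inflammatory. Table 1 in section 1.2 does not support that: with the ranges expanded, it lists 19 inflammatory, 31 interferon and 3 antibody-synthesis genes, so 19 of 53, and no scoring weights are given. The point needs only that the exposure moves some component.

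**Conclusion.** The asymmetry is explicit in both section 6.3 and the synopsis, and sections 15.2, 15.3 and 15.6 do not agree on whether tobacco and alcohol are adjusted for. Followed as written, 15.3 and 15.6 leave unadjusted a potential confounder that the entry rules create.

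The size is illustrative. Under the assumed inputs, the bias in a single-visit level contrast is 0.08-0.40 SD, and the false-positive rate runs from about 6% to about 30%. The effect on slopes should be smaller. The documents give no prevalence, size or direction, so they do not support a claim that the arm comparison is invalid, nor that an observed difference would be due to tobacco or alcohol. They support a narrower conclusion: without adjustment, the arm contrast cannot be attributed to MUD alone. The sponsor should correct this before the SAP is final.

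**What to change.** 1. Reconcile 15.2, 15.3 and 15.6. Add tobacco use and heavy alcohol use to the adjustment sets of 15.3 and 15.6, coded as past-6-month use in the terms of control exclusion 3 and recorded for both arms at screening. State that these coefficients are identified from the CM arm only.
2. Prespecify a sensitivity comparison of controls with those CM participants who would themselves pass the tobacco and alcohol part of control exclusion 3. Report an estimate with a confidence interval, not a significance-based pass or fail. With a true difference of 0.79 SD, this comparison would miss significance about 29%, 38% or 57% of the time at 40%, 60% or 80% exposed, so a null result would often reflect lost sample size.
3. Describe the unadjusted arm contrast as MUD with any accompanying tobacco or alcohol use, against no substance use.

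The cost is SAP wording and one screening question, close to the smoking and alcohol items listed in section 5.4. The question must be in place while participants are being screened. The statistical price is precision: a standard error of about 0.31-0.44 SD in place of 0.28 SD for the restricted comparison, and much the same for the adjusted arm effect.

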## **7 CONCURRENT MEDICATIONS**

All subjects should be maintained on the same medications throughout the entire study period, as medically feasible, with no introduction of new chronic therapies.

### **7.1 Allowed Medications and Treatments**

Standard therapy for HIV (i.e., antiretroviral therapy) is encouraged.

## 8 STUDY TREATMENTS

### 8.1 Method of Assigning Subjects to Treatment Groups

This is a non-randomized behavioral trial with a non-substance-using control group. HIV-positive MSM with methamphetamine use disorder who meet the criteria described above will be assigned to the contingency management treatment group. HIV-positive MSM who do not use substances and meet the criteria described above will be assigned to the non-substance-using control group.

### 8.2 Treatment Schedule

For those with METH use disorder (MA+/HIV+), treatment with CM commences at Visit 1.1, and visits will occur 2x weekly from Weeks 1-8 for regularly urine drug tests (see Table 2). Those in the CM condition will receive escalating rewards for each consecutive negative urine test (Table 2) starting at \$10 and capping at \$40. Participants will receive a \$10 gift card for each visit brief visit where they provide urine tests. Each participant will be allowed to reschedule one appointment 24 hours or more in advance, to take place within 24 hours of the original appointment. Following a missed appointment or relapse, a rapid reset to the participant’s highest reward level will take place by the second consecutive negative urine result. Cash compensation will be provided for key assessment visits at Baseline, Weeks 4, 8, and 12 as shown in Table 2.

Table 2. Compensation for study visits and contingent rewards for negative urine tests

	Visit	Cash for Assessment Visit	Gift Card for Urine Test Only Visit	Consecutive Negative Urine Tests	Contingent Reward
Screen	S	\$40			
Baseline	B	\$50			
Week 1	1.1		\$10	1	\$10
	1.2		\$10	2	\$12
Week 2	2.1		\$10	3	\$14
	2.2		\$10	4	\$16
Week 3	3.1		\$10	5	\$18
	3.2		\$10	6	\$20
Week 4	4.1		\$10	7	\$22
	4.2	\$60		8	\$24
Week 5	5.1		\$10	9	\$26
	5.2		\$10	10	\$28
Week 6	6.1		\$10	11	\$30
	6.2		\$10	12	\$32
Week 7	7.1		\$10	13	\$34
	7.2		\$10	14	\$36
Week 8	8.1		\$10	15	\$38
	8.2	\$80		16	\$40
Week 12	12.0	\$100			
	Subtotal	\$330	\$140		\$400

Those in the non-substance-using control condition (MA-/HIV+) will only attend four appointments total after their screening—one appointment each week at baseline, and Weeks 4, 8, and 12. At these appointments, MA-/HIV+ controls will provide blood draws, urine samples, and complete their behavioral surveys. They will receive attendance compensation at these key visits identical to the CM group (Table 2).

### **8.3 Measures of Treatment Compliance**

Treatment compliance will be based on attendance and urine drug tests, thrice weekly for 8 weeks. Each participant will be allowed to reschedule one appointment 24 hours or more in advance, to take place within 24 hours of the original appointment. Missed visits will be counted as a positive drug test. We will use the in vitro urine drug testing for rapid, simultaneous detection of MA, amphetamine, cocaine, opioids, and MDMA in urine.

## **9 STUDY PROCEDURES AND GUIDELINES**

A Schedule of Events representing the required testing procedures to be performed for the duration of the study is diagrammed in Appendix 1.

Prior to conducting any study-related activities, written informed consent and the Health Insurance Portability and Accountability Act (HIPAA) authorization must be signed and dated by the subject.

### **9.1 Clinical Assessments**

#### **9.1.1 Concomitant Medications**

All concomitant medication and concurrent therapies will be documented at Screening, Baseline, and at Visits 4.2, 8.2, and 12.0. Dose, route, unit frequency of administration, and indication for administration and dates of medication will be captured.

